14.1.2.3 Baseline documentation of target and non-target lesions

For the evaluation of lesions at baseline and throughout the study, the lesions are classified at baseline as either target or non-target lesions:

- **Target lesions:** All measurable lesions (nodal and non-nodal) up to a maximum of five lesions in total (and a maximum of two lesions per organ), representative of all involved

organs should be identified as target lesions and recorded and measured at baseline. Target lesions should be selected on the basis of their size (lesions with the longest diameter) and their suitability for accurate repeated measurements (either by imaging techniques or clinically). Each target lesion must be uniquely and sequentially numbered on the CRF (even if it resides in the same organ).

Minimum target lesion size at baseline

- **Non-nodal target:** Non-nodal target lesions identified by methods for which slice thickness is not applicable (e.g. clinical examination, photography) should be at least 10 mm in longest diameter. See [Section 14.1.2.1.1](#).
- **Nodal target:** See [Section 14.1.2.1.1](#).

A sum of diameters (long axis for non-nodal lesions, short axis for nodal) for all target lesions will be calculated and reported as the baseline sum of diameters (SOD). The baseline sum of diameters will be used as reference by which to characterize the objective tumor response. Each target lesion identified at baseline must be followed at each subsequent evaluation and documented on eCRF.

- **Non-target lesions:** All other lesions are considered non-target lesions, i.e. lesions not fulfilling the criteria for target lesions at baseline. Presence or absence or worsening of non-target lesions should be assessed throughout the study; measurements of these lesions are not required. Multiple non-target lesions involved in the same organ can be assessed as a group and recorded as a single item (i.e. multiple liver metastases). Each non-target lesion identified at baseline must be followed at each subsequent evaluation and documented on eCRF.

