 9. Malignant disease, other than that being treated in this study. Exceptions to this exclusion include the following: malignancies that were treated curatively and have not recurred within 2 years prior to study treatment; completely resected basal cell and squamous cell skin cancers; any malignancy considered to be indolent and that has never required therapy; and completely resected carcinoma *in situ* of any type.
 10. Any medical condition that would, in the investigator's judgment, prevent the patient's participation in the clinical study due to safety concerns, compliance with clinical study procedures or interpretation of study results, including but not limited to:
 - Prior immune-related adverse events requiring treatment discontinuation
 - Ongoing symptomatic interstitial lung disease (ILD), noninfectious pneumonitis or history of drug induced interstitial lung disease
 11. Systemic anti-cancer therapy within 2 weeks or 5 x T $\frac{1}{2}$, whichever is longer of the first dose of study treatment. For cytotoxic agents that have major delayed toxicity, e.g. mitomycin C and nitrosoureas, 4 weeks is indicated as washout period. For patients receiving CTLA-4, PD-1 or PD-L1 antagonists, 6 weeks is indicated as the washout period.
 12. Patients requiring chronic treatment with systemic steroid therapy or any immunosuppressive therapy, other than replacement-dose steroids in the setting of adrenal insufficiency. Any previous steroid or immunosuppressive therapy must be stopped at least 7 days before start of study treatment. Topical, inhaled, nasal and ophthalmic steroids are not prohibited.
 13. Use of any live vaccines against infectious diseases (e.g. varicella, pneumococcus) within 4 weeks of initiation of study treatment.
 14. Major surgery within 2 weeks of the first dose of study treatment (mediastinoscopy, insertion of a central venous access device, and insertion of a feeding tube are not considered major surgery).
 15. Radiotherapy within 2 weeks of the first dose of study drug, except for palliative radiotherapy to a limited field. To allow evaluation for response to treatment, patients enrolled in the Phase II part must have remaining measurable disease that has not been irradiated.
 16. Participation in an interventional, investigational study within 2 weeks of the first dose of study treatment.

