7.1 Study flow and visit schedule

[Table 7-1](#) lists all of the assessments and indicates with an “X”, the visits when they are performed. All data obtained from these assessments must be supported in the patient’s source documentation. The table (“Category” column) indicates which assessments produce data to be entered into the clinical database (D) or remain in source documents only (S).

No CRF will be used as a source document.

Screening/baseline evaluations must be performed ≤ 21 days before Cycle 1 Day 1, except for baseline radiological evaluations which must be done within 28 days. Assessments performed as part of the screening evaluations and within 3 days prior to the first dose of study treatment, are not required to be repeated on the first dosing day.

Laboratory and radiological assessments performed as part of standard of care prior to signing informed consent may be used if performed within 21 days and 28 days respectively, of Cycle 1 Day 1.

During the course of the study visits, test and/or procedures should occur on schedule whenever possible. A visit window of ± 7 days is allowed. If the infusion of MCS110 and/or PDR001 is delayed, the visits assessments will be shifted accordingly. On PK collection days the windows are provided in [Section 7.2.3](#).

Radiological assessments must be performed ± 1 week of the scheduled date of the assessment.

For Japan only, patients are required to be hospitalized during Cycle 1.

Visit name	Category	Protocol Section	Screening Phase	Treatment Phase														Follow-up	Disease Progression F/U	Survival F/U	
			Screening	Cycle 1					Cycle 2		Cycle 3	Cycle 4					Subsequent cycles	EOT			Safety F/U
Day of cycle			-21 to -1	1	2	4	8	15	1	15	1	1	2	4	8	15	1				
Prior/concomitant medications, surgery and medical procedures	D	7.1.1.2 7.1.5 and 6.4	X	Continuous ¹																	
Physical examination	S	7.2.2.1	X	X			X	X	X	X	X	X					X	X			
Height	D	7.2.2.3	X																		
Weight	D	7.2.2.3	X	X					X		X	X					X	X			
Vital signs	D	7.2.2.2	X	X			X	X	X	X	X	X					X	X			
Performance status	D	7.2.2.4	X	X					X		X	X					X	X			
Hematology	D	7.2.2.5.1	X	X			X	X	X	X	X	X			X		X	X			
Chemistry	D	7.2.2.5.2	X	X			X	X	X	X	X	X			X		X	X			
Coagulation	D	7.2.2.5.6	X	Only if clinically significant														X			
Urinalysis	D	7.2.2.5.3	X	X					X		X	X					X	X			
Thyroid function	D	7.2.2.5.4	X	X					X		X	X					X	X			

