14.1.2.1 Definitions

14.1.2.1.1 Disease measurability

In order to evaluate tumors throughout a study, definitions of measurability are required in order to classify lesions appropriately at baseline. In defining measurability, a distinction also needs to be made between nodal lesions (pathological lymph nodes) and non-nodal lesions.

- **Measurable disease** - the presence of at least one measurable nodal or non-nodal lesion. If the measurable disease is restricted to a solitary lesion, its neoplastic nature should be confirmed by cytology/histology.

For patients without measurable disease see [Section 14.1.3.2.8](#)

Measurable lesions (both nodal and non-nodal)

- **Measurable non-nodal** - As a rule of thumb, the minimum size of a measurable non-nodal target lesion at baseline should be no less than double the slice thickness or 10mm whichever is greater - e.g. the minimum non-nodal lesion size for CT/MRI with 5mm cuts will be 10 mm, for 8 mm contiguous cuts the minimum size will be 16 mm.
- **Lytic bone lesions or mixed lytic-blastic lesions with identifiable soft tissue components**, that can be evaluated by CT/MRI, can be considered as measurable lesions, if the soft tissue component meets the definition of measurability.
- **Measurable nodal lesions (i.e. lymph nodes)** - Lymph nodes ≥ 15 mm in short axis can be considered for selection as target lesions. Lymph nodes measuring ≥ 10 mm and < 15 mm are considered non-measurable. Lymph nodes smaller than 10 mm in short axis at baseline, regardless of the slice thickness, are normal and not considered indicative of disease.
- **Cystic lesions:**
 - Lesions that meet the criteria for radiographically defined simple cysts (i.e., spherical structure with a thin, non-irregular, non-nodular and non-enhancing wall, no septations, and low CT density [water-like] content) should not be considered as malignant lesions (neither measurable nor non-measurable) since they are, by definition, simple cysts.
 - ‘Cystic lesions’ thought to represent cystic metastases can be considered as measurable lesions, if they meet the definition of measurability described above. However, if noncystic lesions are present in the same patient, these are preferred for selection as target lesions.

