2.3.3 Other baseline characteristics

Medical history

Medical history and current (ongoing) medical conditions, including cancer-related conditions and symptoms, will be listed. Medical history and current medical conditions are coded using the latest Medical Dictionary for Regulatory Activities (MedDRA v23.0) terminology available at the time of reporting.

Prior anti-neoplastic therapies

Prior anti-neoplastic therapies will be listed for medication, radiotherapy and surgery.

The number (%) of patients who received any prior anti-neoplastic medication, radiotherapy or surgery will be summarized, separately.

The summary of prior anti-neoplastic medications will include the total number of regimens (note: there can be more than one medication per regimen), setting at last medication, and time (in days) from start of last medication to progression.

The last medication is defined based on the last end date of all prior regimen components. Prior antineoplastic medications will also be summarized by Anatomical Therapeutic Chemical (ATC) class, and preferred term.

The summary of prior anti-neoplastic radiotherapy will include the radiotherapy locations, (including all locations recorded for each patient) and setting at last radiotherapy.

The summary of prior anti-neoplastic surgery will include the time (in months) between the last surgery (non-biopsy procedure) to start of study treatment, procedure at last surgery (non-biopsy procedure) and residual disease at last surgery.

Consider specific imputation rules for partial dates in [Section 5.1.4](#).

Diagnosis and extent of cancer

The summary and listing of diagnosis and extent of cancer (disease history) will include primary site of cancer, histological grade, stage at initial diagnosis, time (in months) from initial diagnosis of primary site to start of study treatment, time (in months) since most recent recurrence/relapse or progression to start of study treatment, time (in months) from initial diagnosis of primary site to first recurrence/relapse or progression, current stage of cancer, current extent of disease (metastatic sites).

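### Recently irradiated lesions are not barred from being target lesions, so radiotherapy shrinkage can count as response to MCS110 + PDR001; a sensitivity analysis should show whether it did

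*Protocol*

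**What the plan says.** **Eligibility.** Protocol 5.3, criterion 15, excludes "Radiotherapy within 2 weeks of the first dose of study drug, except for palliative radiotherapy to a limited field". The exempted radiotherapy has no minimum interval before the first dose. So that response can be evaluated, the criterion adds that "patients enrolled in the Phase II part must have remaining measurable disease that has not been irradiated". Phase Ib has no such condition, although ORR is a secondary endpoint there.

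**Baseline scan.** Screening assessments fall within 21 days of Cycle 1 Day 1, "except for baseline radiological evaluations which must be done within 28 days" (Protocol 7.1).

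**Target lesions.** Protocol 14.1.2.1.1 defines measurable disease as "the presence of at least one measurable nodal or non-nodal lesion". Protocol 14.1.2.3 takes as targets "All measurable lesions (nodal and non-nodal) up to a maximum of five lesions in total", with at most two per organ, and adds: "Target lesions should be selected on the basis of their size (lesions with the longest diameter) and their suitability for accurate repeated measurements". Neither section mentions prior irradiation. Appendix 2 (14.2.1) adopts the same baseline lesion definitions for irRC.

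**Scoring.** PR is a fall of at least 30% from baseline in the sum of diameters over all targets (Table 14-1).

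**Analysis.** SAP 2.3.3 says "The summary of prior anti-neoplastic radiotherapy will include the radiotherapy locations" and the setting of the last course. Nothing links these data to target lesions. SAP 2.5.4 plans no supportive analysis.

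**The concern.** Criterion 15 recognises that irradiated lesions are a problem for response evaluation, but the response rules do not carry the thought through. An unirradiated lesion must exist in Phase II; nothing ties the response to it. The irradiated lesion may sit in the same sum. Radiotherapy may even fall between the baseline scan and the first dose, in which case the baseline measurement predates it.

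ORR (Groups 1, 3, 4) and CBR (Group 2) are primary endpoints of uncontrolled groups, so no comparator would reveal a radiotherapy effect. There are two routes to error: shrinkage of an irradiated target lifts the patient to PR, or it offsets growth in unirradiated targets so that progression on the sum is missed.

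**Working it through.** **1. When can an irradiated target produce a PR?** Let I and U be the baseline irradiated and unirradiated target sums, and s the fractional shrinkage of I, with U unchanged. The change in the sum is -I·s/(I+U). A PR needs s of at least 0.30 × (I+U)/I, which is possible only if I is at least 30% of the sum. The diameters are illustrative.

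| I + U (mm) | s | Change | Result |
|---|---|---|---|
| 50 + 30 | 50% | -25/80 = -31% | PR |
| 40 + 40 | 60% | -24/80 = -30% | PR |
| 20 + 60 | 100% | -20/80 = -25% | not PR |

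**2. Masking.** In the 50 + 30 mm case, let the irradiated lesion halve to 25 mm and the other grow from 30 to 50 mm (+67%, progression if it were the only target). The first follow-up sum is 75/80, or -6%: SD on targets.

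**3. The plan's own figures.** Inputs are the expansion and success rules in Protocol 10.4.2.2 and 10.8. The gate is P(X ≥ r1) with X ~ Bin(20, p). Overall success is the sum over x ≥ r1 of P(X = x) × P(Bin(20, p) ≥ r - x). Group 4 (r1 = 2, r = 6, p = 7.5%) gives 44.9% and 7.1%. Groups 1 and 3 (r1 = 3, r = 12, p = 15%) give 59.5% and 1.2%. These match Tables 10-3 and 10-2.

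**4. One carry-over PR among the first 20 (assumed).** The other 19 respond at the true rate, so r1 and r each fall by one and the first stage is Bin(19, p).

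- Group 4 gate: 1 - 0.925^19 = 77.3%. Overall success: 16.2%.
- Groups 1 and 3 gate: 1 - 0.85^19 - 19 × 0.15 × 0.85^18 = 80.2%. Overall success: 2.5%.

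**5. Range.** If a fraction f of true non-responders has a carry-over PR, the apparent rate is p + (1 - p)f.

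| f (assumed) | Group 4 success, p = 7.5% | Groups 1 and 3 success, p = 15% |
|---|---|---|
| 0 | 7.1% | 1.2% |
| 1% | 10.9% | 1.8% |
| 2.5% | 18.2% | 3.2% |
| 5% | 33.6% | 6.9% |

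**6. What is still live.** The study status in Amendment 05 reports 20 pancreatic, 20 TNBC, 21 endometrial and 20 melanoma patients, with no expansion criterion met. One patient is worth 1/20 = 5.0 or 1/21 = 4.8 points. With the Group 2 and Group 4 prior Beta(0.18, 1), x successes in 20 give the posterior Beta(0.18 + x, 21 - x). The probability of the unacceptable category (below 7.5%) is 98% for x = 0, 73% for x = 1 and 40% for x = 2.

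**The case against.** The strongest reply is that the damage to the design did not occur: no group expanded, so no carry-over response opened a gate or reached a 40-patient success rule. That stands. Steps 3 to 5 therefore describe a weakness of the design, not an event in this trial. Expansion was also not automatic, since Protocol 10.7 calls for a synthesis of all data.

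Other provisions narrow the gap without closing it.

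- Inclusion criterion 4 requires progression after the last prior therapy. That progression may be in other lesions, or may precede palliative radiotherapy given for symptoms.
- Protocol 6.4.2 bars other active anticancer therapy during the study. Radiotherapy before consent is not reached.
- Confirmation after 4 weeks (7.2.1) does not remove lasting shrinkage.
- The unirradiated lesion required in Phase II means that irradiated lesions alone cannot give a CR, and it caps the effect on PR as step 1 shows.

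CBR is less exposed than ORR. SD beyond 4 months already counts as benefit, so turning such SD into PR changes nothing. CBR moves only through masked progression or through a confirmed PR that progresses before 4 months.

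A reader might also infer that Appendix 1 expressly includes irradiated lesions, or that they will usually be the largest targets. Neither is supported: the text is silent on irradiation, caps the number of targets, wants them to represent all involved organs, and says nothing about the size of irradiated lesions.

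**Conclusion.** The gap is real. Followed as written, the plan can credit radiotherapy shrinkage to the combination, and no planned analysis would show it. The documents give no frequency of recent palliative radiotherapy to target lesions, so the number of affected patients may be zero. The gate and success figures rest on an assumed one patient in 20, or on the assumed range of f.

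It would be tempting to conclude that the trial expanded wrongly or that its reported rates are inflated. The documents do not support either. If the statement that no criterion was met covers all observed responses, Group 4 had at most one responder and the other groups at most two patients meeting their criterion, which also bounds the number of carry-over successes. Within that bound one patient still matters: about 5 points on ORR or CBR, and a fall from 98% to 73% (Group 4, no responder against one) or from 73% to 40% (Group 2, one against two) in the probability of unacceptable efficacy. That is enough to justify a check, but not to replace the primary analysis.

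**What to change.** Keep the primary analysis. Replace the empty SAP 2.5.4 with a sensitivity analysis specified before database lock:

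- Identify target lesions in a field irradiated before the first dose and not shown to have progressed since, using the radiotherapy locations and dates already collected. Include radiotherapy given after the baseline scan.
- Leave those lesions out of the sum of diameters at baseline and at every follow-up, so that their omission does not make an assessment unknown.
- Re-derive RECIST v1.1 and irRC response, ORR or CBR, and the Bayesian posterior with its category probabilities.
- Report the number of patients affected in each group, including when it is zero.

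If the database is already locked, SAP section 1 provides for an addendum, and the analysis should be labelled post hoc.

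For consistency with the aim of criterion 15, add one sentence to Protocol 14.1.2.3, and to Appendix 2 by reference, that such lesions are followed as non-target. This changes nothing for patients already enrolled but closes the gap if the text is reused.

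The cost is some manual matching of radiotherapy site to numbered lesion, and fewer target lesions in a few patients. Phase II patients should stay evaluable because criterion 15 already requires unirradiated measurable disease. The washout rule itself is left as it is.

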14.1.2.4 Follow-up evaluation of target and non-target lesions

To assess tumor response, the sum of diameters for all target lesions will be calculated (at baseline and throughout the study). At each assessment response is evaluated first separately for the target ([Table 14-1](#)) and non-target lesions ([Table 14-2](#)) identified at baseline. These evaluations are then used to calculate the overall lesion response considering both the target and non-target lesions together ([Table 14-3](#)) as well as the presence or absence of new lesions.

14.1.2.4.1 Follow-up and recording of lesions

At each visit and for each lesion the actual date of the scan or procedure which was used for the evaluation of each specific lesion should be recorded. This applies to target and non-target lesions as well as new lesions that are detected. At the assessment visit all of the separate lesion evaluation data are examined by the investigator in order to derive the overall visit response. Therefore all such data applicable to a particular visit should be associated with the same assessment number.

Non-nodal lesions

Following treatment, lesions may have longest diameter measurements smaller than the image reconstruction interval. Lesions smaller than twice the reconstruction interval are subject to substantial “partial volume” effects (i.e., size may be underestimated because of the distance of

the cut from the longest diameter; such lesions may appear to have responded or progressed on subsequent examinations, when, in fact, they remain the same size).

If the lesion has completely disappeared, the lesion size should be reported as 0 mm.

Measurements of non-nodal target lesions that become 5 mm or less in longest diameter are likely to be non-reproducible. Therefore, it is recommended to report a default value of 5 mm, instead of the actual measurement. This default value is derived from the 5 mm CT slice thickness (but should not be changed with varying CT slice thickness). Actual measurement should be given for all lesions larger than 5 mm in longest diameter irrespective of slice thickness/reconstruction interval.

In other cases where the lesion cannot be reliably measured for reasons other than its size (e.g., borders of the lesion are confounded by neighboring anatomical structures), no measurement should be entered and the lesion cannot be evaluated.

Nodal lesions

A nodal lesion less than 10 mm in size by short axis is considered normal. Lymph nodes are not expected to disappear completely, so a “non-zero size” will always persist.

Measurements of nodal target lesions that become 5 mm or less in short axis are likely to be non-reproducible. Therefore, it is recommended to report a default value of 5 mm, instead of the actual measurement. This default value is derived from the 5 mm CT slice thickness (but should not be changed with varying CT slice thickness). Actual measurement should be given for all lesions larger than 5 mm in short axis irrespective of slice thickness/reconstruction interval.

However, once a target nodal lesion shrinks to less than 10 mm in its short axis, it will be considered normal for response purpose determination. The lymph node measurements will continue to be recorded to allow the values to be included in the sum of diameters for target lesions, which may be required subsequently for response determination.

14.1.2.4.2 Determination of target lesion response

Table 14-1 Response criteria for target lesions

Response Criteria	Evaluation of target lesions
Complete Response (CR):	Disappearance of all non-nodal target lesions. In addition, any pathological lymph nodes assigned as target lesions must have a reduction in short axis to < 10 mm ¹
Partial Response (PR):	At least a 30% decrease in the sum of diameter of all target lesions, taking as reference the baseline sum of diameters.
Progressive Disease (PD):	At least a 20% increase in the sum of diameter of all measured target lesions, taking as reference the smallest sum of diameter of all target lesions recorded at or after baseline. In addition to the relative increase of 20%, the sum must also demonstrate an absolute increase of at least 5 mm ² .
Stable Disease (SD):	Neither sufficient shrinkage to qualify for PR or CR nor an increase in lesions which would qualify for PD.
Unknown (UNK)	Progression has not been documented and one or more target lesions have not been assessed or have been assessed using a different method than baseline. ³

¹. SOD for CR may not be zero when nodal lesions are part of target lesions

². Following an initial CR, a PD cannot be assigned if all non-nodal target lesions are still not present and all nodal lesions are <10 mm in size. In this case, the target lesion response is CR

³. Methodology change See [Section 14.1.2.2](#)

Notes on target lesion response

Reappearance of lesions: If the lesion appears at the same anatomical location where a target lesion had previously disappeared, it is advised that the time point of lesion disappearance (i.e., the “0 mm” recording) be re-evaluated to make sure that the lesion was not actually present and/or not visualized for technical reasons in this previous assessment. If it is not possible to change the 0 value, then the investigator/radiologist has to decide between the following three possibilities:

- The lesion is a new lesion, in which case the overall tumor assessment will be considered as progressive disease
- The lesion is clearly a reappearance of a previously disappeared lesion, in which case the size of the lesion has to be entered in the CRF and the tumor assessment will remain based on the sum of tumor measurements as presented in [Table 14-1](#) above (i.e., a PD will be determined if there is at least 20% increase in the sum of diameters of **all** measured target lesions, taking as reference the smallest sum of diameters of all target lesions recorded at or after baseline with at least 5 mm increase in the absolute sum of the diameters). Proper documentation should be available to support this decision. This applies to patients who have not achieved target response of CR. For patients who have achieved CR, please refer to last bullet in this section.
- For those patients who have only one target lesion at baseline, the reappearance of the target lesion which disappeared previously, even if still small, is considered a PD.
- **Missing measurements:** In cases where measurements are missing for one or more target lesions it is sometimes still possible to assign PD based on the measurements of the remaining lesions. For example, if the sum of diameters for 5 target lesions at baseline is 100 mm at baseline and the sum of diameters for 3 of those lesions at a post-baseline visit is 140 mm (with data for 2 other lesions missing) then a PD should be assigned. However, in other cases where a PD cannot definitely be attributed, the target lesion response would be UNK.
- **Nodal lesion decrease to normal size:** When nodal disease is included in the sum of target lesions and the nodes decrease to “normal” size they should still have a measurement recorded on scans. This measurement should be reported even when the nodes are normal in order not to overstate progression should it be based on increase in the size of nodes.
- **Lesions split:** In some circumstances, disease that is measurable as a target lesion at baseline and appears to be one mass can split to become two or more smaller sub-lesions. When this occurs, the diameters (long axis - non-nodal lesion, short axis - nodal lesions) of the two split lesions should be added together and the sum recorded in the diameter field on the case report form under the original lesion number. This value will be included in the sum of diameters when deriving target lesion response. The individual split lesions will not be considered as new lesions, and will not automatically trigger a PD designation.

- **Lesions coalesced:** Conversely, it is also possible that two or more lesions which were distinctly separate at baseline become confluent at subsequent visits. When this occurs a plane between the original lesions may be maintained that would aid in obtaining diameter measurements of each individual lesion. If the lesions have truly coalesced such that they are no longer separable, the maximal diameters (long axis - non-nodal lesion, short axis - nodal lesions) of the “merged lesion” should be used when calculating the sum of diameters for target lesions. On the case report form, the diameter of the “merged lesion” should be recorded for the size of one of the original lesions while a size of “0”mm should be entered for the remaining lesion numbers which have coalesced.
- The **measurements for nodal lesions**, even if less than 10 mm in size, will contribute to the calculation of target lesion response in the usual way with slight modifications.
- Since lesions less than 10 mm are considered normal, a CR for target lesion response should be assigned when all nodal target lesions shrink to less than 10 mm and all non-nodal target lesions have disappeared.
- Once a CR target lesion response has been assigned a CR will continue to be appropriate (in the absence of missing data) until progression of target lesions.
- Following a CR, a PD can subsequently only be assigned for target lesion response if either a non-nodal target lesion “reappears” or if any single nodal lesion is at least 10 mm and there is at least 20% increase in sum of the diameters of all nodal target lesions relative to nadir with at least 5 mm increase in the absolute sum of the diameters.

